### 8.1.4 Adverse Device Effect (ADE)

An adverse event related to the use of a study device.

This definition includes adverse events resulting from insufficient or inadequate instructions for use, deployment, implantation, installation, or operation, or any malfunction of the study device.

This definition includes any event resulting from the use error or from intentional misuse of the study device.

### 8.1.5 Serious Adverse Device Effect (SADE)

Adverse device effect that has resulted in any of the consequences characteristic of a serious adverse event.

### 8.1.5.1 Unanticipated Serious Adverse Device Effect (USADE)

A serious adverse device effect which, by its nature, incidence, severity, or outcome has not been identified in the current version of the risk analysis report.

### 8.1.6 Device relationship

Determination of whether there is a reasonable possibility that a study device caused or contributed to an AE will be determined by the Investigator and recorded on the appropriate CRF. Determination should be based on assessment of temporal relationships, evidence of alternative etiology, medical/biologic plausibility, and patient condition (pre-existing condition).

### 8.2 Procedure for assessing, recording and reporting AEs, ADEs, SADEs:

Safety surveillance within this study and the safety reporting, both performed by the Investigator, starts as soon as the subject is enrolled in this study (date of signature of the informed consent). The safety surveillance and the safety reporting will continue until the last study visit has been performed, the subject is deceased, the subject/Investigator concludes his participation in the study or the subject/Investigator withdraws the subject from the study.

Records related to the subject's subsequent medical course must be maintained and submitted (as applicable) to the Sponsor until the event has subsided or, in case of permanent impairment, until the event stabilizes and the overall clinical outcome has been ascertained. Adverse events will be monitored until they are adequately resolved. The status of the subject's condition should be documented at each visit.

Adverse event data will be collected throughout the clinical study and will be reported to the Sponsor on a dedicated case report form.

Reportable events to sponsor are considered:

- 1. All Serious Adverse Events
- 2. All procedure- (e.g., MRI scan) or device-related Adverse Events (whether or not the event is considered serious).

### SAE Reporting

The investigator should report all SAEs to the Sponsor as soon as possible but no later than outlined below.

	Clinical Site	Reporting timelines		
SJM-CI	P-10056		Page 27 of	of 49

## **Clinical Investigation Plan**

All Sites	SAEs must be reported to the Sponsor no later than 3 calendar days from the day
	the site personnel became aware of the event or as per the investigative site's local
	requirements, if the requirement is more stringent than those outlined.

The date the site staff became aware the event met the criteria of an SAE must be recorded in the source document. The Investigator will further report the SAE to the local IRB/EC according to the institution's IRB/EC reporting requirements.

The Sponsor will ensure that all events are reported to the relevant authorities as per regulations.

### Foreseeable Adverse Effects

In addition to the adverse events commonly associated with surgery, the following adverse effects are associated with implanting or using the neurostimulation for SCS.

List of foreseeable adverse effects:

- Unpleasant sensations or motor disturbances, including involuntary movement, caused by stimulation at high outputs (if either occurs, turn off the IPG immediately)
- Undesirable changes in stimulation, which may be related to cellular changes in tissue around the electrodes, changes in electrode position, loose electrical connections, or lead failure
- Stimulation in unwanted places
- Lead migration, causing changes in stimulation or reduced pain relief
- Epidural hemorrhage, hematoma, infection, spinal cord compression, or paralysis from placement of a lead in the epidural space
- Cerebrospinal fluid (CSF) leakage
- Paralysis, weakness, clumsiness, numbness, or pain below the level of the implant
- Persistent pain at the electrode or IPG site
- Seroma (mass or swelling) at the IPG site
- Allergic or rejection response to implant materials
- Implant (IPG) migration or skin erosion around the implant
- Battery failure or battery leakage

Changes in stimulation parameters may occur due to the failure of, or changes in, components over time, which results in:

- Understimulation
- Return of underlying symptoms
- Overstimulation
- Premature battery depletion
- The need to explant the device

The following potential adverse effects may occur in the MRI environment:

- Lead electrode heating resulting in tissue damage or serious subject injury
- IPG heating resulting in tissue damage in the implant pocket, or subject discomfort, or both
- Induced currents on leads resulting in overstimulation or shocking sensations
- Damage to the IPG or leads causing the system to fail deliver stimulation or causing the system to deliver overstimulation
- Damage to the functionality or mechanical integrity of the IPG resulting in the inability to communicate with the IPG

• Movement or vibration of the IPG or leads

Abbott

In addition, subjects may experience unavoidable events related to the MRI scan. An unavoidable event is an event related to the MRI scan that may occur for a projected duration in any subject. Unavoidable events are expected to occur with any MRI scan and are not reportable unless the condition worsens or continues beyond the timeframe listed below. Unavoidable events do not need to be reported on an Adverse Event form if they are resolved within the time frame specified.

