### 4.6 Endpoints

### 4.6.1 **Primary endpoint**

The primary endpoint is the rate of MRI scan-related adverse events.

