### 6.12 Any known or foreseeable factors that may compromise the outcome

All foreseeable factors that may compromise the outcome of the clinical study or the interpretation of the results have been accounted for by clinical study design and well-defined subject selection criteria.

Subject recruitment and retention will be mastered throughout the study and include (but are not limited to) the following activities: evaluation of the site and Investigators, training of site personnel, developing site support materials, providing subject visit calendars.

A Clinical Events Committee (CEC) will be formed as best practice to ensure that the primary outcome is as free from bias as possible. The CEC will review and adjudicate reportable adverse events as defined in the CEC charter for seriousness, device-relatedness, and MRI-relatedness.

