### 8.1.2 Adverse Event (AE)

An adverse event (AE) is any untoward medical occurrence, unintended disease or injury, or untoward clinical signs (including abnormal laboratory findings) in subjects, users, or other persons, whether or not related to the medical device under study.

Note 1: This definition includes events related to the medical device under study.

Note 2: This definition includes events related to the procedures involved.

**Note 3:** For users or other persons, this definition is restricted to events related to medical devices under investigation.

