### Table 3. List of unavoidable MRI-related events

Event	Timeframe
Claustrophobia	During MRI scan
Mild diaphoresis	During and < 1-hour post MRI scan
Sensation of bodily warmth	During and < 1-hour post MRI scan
Sensation of warmth at device pocket not arising to the level of discomfort	During and < 1-hour post MRI scan
Hearing Impairment	< 24 hours post MRI scan
Body Stiffness related to immobility	< 48 hours post MRI scan

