### **12.0 STATISTICAL CONSIDERATIONS**

### 12.1 Statistical design, hypotheses, method and analytical procedures

This is a prospective, multicenter, and single arm study.

• Analysis for primary endpoint

The primary endpoint is the event rate of MRI scan-related adverse events. The hypothesis is formally expressed as:

H0: MRI scan-related adverse event rate  $\geq 10\%$ 

H1: MRI scan-related adverse event rate < 10%

MRI-scan related adverse event rate will be summarized as the proportion of subjects who have of MRI-scan related events. The primary endpoint will be tested at the 5% significance level. The null hypothesis will be rejected if the 95% UCB for MRI scan-related adverse event rate is less than 0.10. Confidence intervals will be calculated based on the Clopper-Pearson exact method for binomial proportion.

The performance goal of 10% is based on performance goals used by historical MRI safety studies.  $^{14\text{-}17}$ 

• Analysis for secondary endpoint

The success of each of secondary endpoint will be summarized as the number of success and its percentage, together with its 95% confidence interval estimated using Clopper-Pearson exact method for binomial distribution.

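### Does leaving short-lived, expected scan symptoms off the Adverse Event form undermine the primary endpoint?

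*Combined protocol and SAP*

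**What the plan says.** Section 4.6.1 reads: "The primary endpoint is the rate of MRI scan-related adverse events". Section 12.1 repeats this and gives the summary measure: "MRI-scan related adverse event rate will be summarized as the proportion of subjects who have of MRI-scan related events". Neither section mentions Table 3.

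Section 8.2 first makes every procedure-related or device-related adverse event reportable to the sponsor, serious or not, and names the MRI scan as an example of a procedure. Under Foreseeable Adverse Effects it then carves out a class of scan-related symptoms: "Unavoidable events are expected to occur with any MRI scan and are not reportable unless the condition worsens or continues beyond the timeframe listed below". It adds: "Unavoidable events do not need to be reported on an Adverse Event form if they are resolved within the time frame specified".

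Table 3 lists six: claustrophobia, mild diaphoresis, bodily warmth, pocket warmth, hearing impairment and stiffness from lying still. The windows run from the scan itself to under 48 hours afterwards. The pocket item is worded "Sensation of warmth at device pocket not arising to the level of discomfort".

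Section 6.12 sets up a Clinical Events Committee to keep the primary outcome as free of bias as possible: "The CEC will review and adjudicate reportable adverse events as defined in the CEC charter for seriousness, device-relatedness, and MRI-relatedness". Section 12.10, on information excluded from the hypothesis test, is answered as not applicable.

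**The concern.** Read alone, the endpoint sections cover all scan-related events. Section 8.2 calls the Table 3 symptoms scan-related yet keeps them off the form that feeds the endpoint. The trial could then report a scan-related adverse event rate below 10% without having counted some scan-related events, and a reader of sections 4.6.1 and 12.1 alone would not know.

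Two features sharpen the worry. The decision rule tolerates only one affected subject in 46, so moving two subjects across the boundary reverses the result. And one exempted symptom, warmth at the device pocket, lies close to a hazard the plan lists for the MRI environment: "IPG heating resulting in tissue damage in the implant pocket, or subject discomfort, or both". The visit schedule, the data lists and section 12 describe no count of exempted symptoms.

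**Working it through.** **Inputs.** Sections 12.1 and 12.2: performance goal 10%, assumed true rate 1%, one-sided 5% level, Clopper-Pearson exact bound, 46 scans with one per subject, 5% dropout before the scan.

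**The plan's own figures.** With X the number of subjects with an event, the rule rejects when the one-sided 95% upper bound is below 10%. At n = 46 the bounds are:

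| Subjects with an event | Upper bound | Result |
|---|---|---|
| 0 | 6.30% | pass |
| 1 | 9.90% | pass |
| 2 | 13.06% | fail |

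The rule is therefore X ≤ 1.

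- Type I error: P(X ≤ 1 | 46, 0.10) = 0.9^46 + 46 × 0.1 × 0.9^45 = 0.0079 + 0.0401 = 0.0480.
- Power at 1%: P(X ≤ 1 | 46, 0.01) = 0.99^46 + 46 × 0.01 × 0.99^45 = 0.6298 + 0.2927 = 0.9225.
- At n = 45 only X = 0 passes, and power is 0.99^45 = 0.6362. The smallest n with at least 80% power is 46, as planned.
- Enrolment: 46/0.95 = 48.42, rounded up to 49, as planned.

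**What if the exempted symptoms counted?** The documents give no frequency, so the added share q of subjects is purely an assumption, taken as independent of the 1% base rate. The event probability becomes p = 1 − 0.99 × (1 − q), and the chance of passing is P(X ≤ 1 | 46, p):

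| q | p | Chance of passing |
|---|---|---|
| 0 | 1.00% | 92.2% |
| 1% | 1.99% | 76.7% |
| 2% | 2.98% | 60.0% |
| 5% | 5.95% | 23.3% |
| 10% | 10.90% | 3.3% |

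So the boundary matters. The question is whether the documents leave it open.

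**Setting the sections side by side.**

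1. Section 8.2 makes Table 3 symptoms non-reportable unless they worsen or outlast their window. Section 6.12 has the committee judge MRI-relatedness for reportable events, and ties that review to the primary outcome. Together they make the primary rate a rate of reportable events.
2. The planning rate agrees. Section 12.2 assumes 1%, while section 8.2 describes Table 3 symptoms as expected with any scan. A 1% rate is plausible only if such symptoms are not counted.
3. Section 8.1.2 defines an adverse event as "any untoward medical occurrence, unintended disease or injury, or untoward clinical signs". Warmth without discomfort is hard to call untoward, so for the two warmth items arguably nothing leaves the named endpoint. This argument is weaker for claustrophobia and hearing impairment.
4. Table 3 exempts pocket warmth only below discomfort and only up to one hour after the scan. The listed hazard starts at discomfort or tissue damage. The two entries meet at a stated threshold and do not overlap. Warmth that reaches discomfort, worsens or lasts an hour or more is reportable.
5. Symptoms never collected as adverse events are not data withheld from the test, so the entry in section 12.10 is defensible.

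**The case for a change.** The strongest opposing case is that the null and alternative hypotheses in section 12.1 are worded without qualification, and that its summary measure speaks of scan-related events, the same relation that section 8.2 gives to Table 3 symptoms. A safety study whose results go to a Notified Body should say plainly what its headline rate covers. Whether pocket warmth amounts to discomfort is a judgement at the site, and the protocol describes no record against which to check it.

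Part of this stands. The endpoint sections carry no cross-reference to Table 3, and a sentence there would have spared the reader the search. It would not alter any count, since the sections read together lead to one answer.

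The missing tally is less certain than it looks. Appendices D and H place the questionnaire and the case report forms under separate cover, and section 6.12 refers to a committee charter; any of these may record the symptoms. Sites must also check for scan-related adverse events at every visit after enrolment (section 6.2), and they cannot apply Table 3 without asking whether a symptom worsened or resolved in time.

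A supplementary rate including Table 3 symptoms would add little. It would mix claustrophobia and stiffness with pocket warmth, has no non-implanted comparator, and would be imprecise: 2 of 46 gives a two-sided 95% interval of 0.53% to 14.84%, and 5 of 46 gives 3.62% to 23.57%. Asking again at one month about symptoms limited to 48 hours would bring recall error.

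**Conclusion.** No change to the plan follows. The exemption is stated in advance in section 8.2, and Appendix B records it as a deliberate addition. The reporting rule and the committee's remit together fix what the primary rate counts. For that endpoint the test is valid, with type I error 4.80% against a 5% limit and power 92.2% against a stated 80%, and the planned 46 and 49 subjects both reproduce. What remains is a cross-reference that analysts will supply, and a tally that the protocol does not describe but the forms may hold. Neither produces a wrong result.

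This rests on two assumptions: that the committee charter defines reportable events as section 8.2 does, and that the report describes the rate as one of reportable events. The documents do not say how the historical studies behind the 10% goal treated such symptoms, so nothing here relies on them. With no frequency given for Table 3 symptoms, the passing probabilities above show sensitivity under assumed shares and do not estimate any bias.

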### Table 3. List of unavoidable MRI-related events

Event	Timeframe
Claustrophobia	During MRI scan
Mild diaphoresis	During and < 1-hour post MRI scan
Sensation of bodily warmth	During and < 1-hour post MRI scan
Sensation of warmth at device pocket not arising to the level of discomfort	During and < 1-hour post MRI scan
Hearing Impairment	< 24 hours post MRI scan
Body Stiffness related to immobility	< 48 hours post MRI scan

### 8.2.1 Procedure for recording and reporting subject death

All subject deaths that occur during this study must be reported to Abbott within 3 calendar days of the site being notified (refer to Section 8.2). Notification of a death should include a detailed statement of the pertinent events and be signed by the investigator in addition to the completion of the appropriate forms (Death form and Withdrawal form) and submitted to Abbott using the paper CRFs in this study. It is the Investigator's responsibility to notify the IRB/EC per the IRB/EC policy.

### 8.3 Device Deficiency (DD)

A device deficiency is defined as an inadequacy of a medical device with respect to its identity, quality, durability, reliability, safety or performance. Device deficiencies include malfunctions, use errors, and inadequate labeling.

Device deficiencies are not collected in this study. While some device functionality information will be collected as secondary endpoints (Section 4.6.2), the device deficiency reporting instructions below should be followed for all device deficiencies identified during this study.

If the device deficiency does not involve an AE, the Investigator must notify the Abbott Post Market Surveillance Department by submitting the complaint information via email to [contact] or by [contact] as soon as possible after becoming aware of the complaint.

### 9.0 DATA MANAGEMENT

Overall, the Sponsor will be responsible for the data handling.

The sponsor and/or its affiliates will be responsible for compiling and submitting all required reports to governmental agencies.

Data will be analyzed by the Sponsor and may be transferred to the Sponsor's locations outside of Europe and/or any other worldwide regulatory authority in support of a market-approval application.

The Principal Investigator or institution will provide direct access to source data during and after the clinical study for monitoring, audits, IRB/EC review, and regulatory authority inspections. As required, the Principal Investigator or institution will obtain permission for direct access to source documents from the subject, hospital administration, and national regulatory authorities before starting the clinical study.

### 9.1 Protection of personally identifiable information

The Sponsor respects and protects personally identifiable information collected or maintained for this clinical investigation.

The Sponsor implements technical and physical access controls to ensure that Personal Information is accessible only to and processed only on a 'need to know' basis, including periodic review of access rights, and revocation of access when an individual's employment is terminated or the individual transitions to a role that does not require access to Personal Information, and appropriate restrictions on physical access to premises, facilities, equipment, and records containing Personal Information.

The Sponsor requires the investigational sites to transfer into Sponsor's data management systems only pseudonymous Personal Information (key-coded) necessary to conduct the Clinical Investigation, such as the patient's medical condition, treatment, dates of treatment, etc. The Sponsor discloses as part of the clinical investigation informed consent process that some Sponsor representatives still may see Personal Information at the participating sites for technical support of the participating physicians on the device implant or procedures, monitoring and quality control purposes. Confidentiality of Personal Information will be observed by all parties involved at all times throughout the clinical investigation. The privacy of each subject and confidentiality of his/her information will be preserved in reports and when publishing any data.

The Sponsor data management systems and processes were designed, developed, and tested according to industry standards to appropriately safeguard Confidential Information (including any Personal Information) against unauthorized access and/or interference by third parties, intrusion, theft, destruction, loss or alteration. Clinical Investigation data are encrypted in transit and at rest.

The Sponsor maintains a Privacy Incident procedure that complies in all respects with Applicable Law and industry best practices.

### 9.2 Data management plan

A detailed Data Management Plan will be established to ensure consistency of the data. This document will include procedures used for data review, database cleaning, and issuing and resolving data queries. If appropriate, the DMP may be updated throughout the study duration. All revisions will be tracked and document controlled.

CRF data will be captured in a validated electronic database management Oracle Clinical system hosted by Abbott.

Only authorized site personnel will be permitted to enter the data on paper CRFs provided by Abbott.

### 9.3 Document and data control

### 9.3.1 Traceability of documents and data

The Investigator shall ensure accuracy, completeness, legibility, and timeliness of the data reported to the sponsor on the CRFs and in all required reports. Where copies of the original source document as well as printouts of original electronic source documents are retained, these shall be signed and dated by a member of the investigation site team with a statement that it is a true reproduction of the original source document.

### 9.3.2 Recording data

Source documents shall be created and maintained by the investigation site team throughout the clinical study. The data reported on the CRFs shall be derived from, and be consistent with, these source documents, and any discrepancies shall be explained in writing.

The CRFs shall be validated by the Principal Investigator or designee. In case of modifications after the validation, the CRFs should be re-approved by the Investigator or designee.

### **10.0 MONITORING**

It is the responsibility of Abbott, as the sponsor of the study, to ensure the study is conducted, recorded, and reported according to the approved protocol, subsequent amendment(s), applicable regulations, and guidance documents. Monitoring will be conducted according to the Abbott Clinical Monitoring standard operating procedure.

Prior to beginning the study, Abbott will contact the Investigator or designee to discuss the study and data requirements. An Abbott monitor will periodically review the subject records and associated source documents.

The Investigator shall make subject and study records available to the clinical monitor for monitoring.

